	
 
The PD population will consist of all subjects who receive at least one dose of study drug and have post-dose PD data available.
 
 
Primary safety analyses will be performed on the ITT population. Demographics, subject disposition, and screening and baseline characteristics will be summarized for the PK and ITT populations, where appropriate.
 
Criteria for evaluation
 
  
 Objective	Endpoint	
   
 Primary	
 
 Safety and tolerability of 5 once-weekly IV infusions of SYNT001 to subjects with pemphigus vulgaris or foliaceus	AEs and clinical (safety) laboratory tests	
 
 Secondary	
 
 PK of SYNT001 following a 1-hour IV infusion	PK parameters: <math>t_{1/2}</math>, <math>C_{max}</math>, <math>T_{max}</math>, <math>AUC_{0-24}</math>, and <math>AUC_{0-\infty}</math>.	
 
 Effect of 5 once-weekly IV doses of SYNT001 on:           
 
Total IgG (IgG1-4), IgA, IgM, and albumin
 
Serum anti-Dsg (1 and 3) antibodies
 
 	Changes in levels of IgG, IgG subtypes (IgG1-4), IgA, IgM, albumin, serum anti-Dsg (1 and 3) antibodies	
 
 Assess immunogenicity	Anti-SYNT001 antibodies	
 
 Disease Activity	PDAI Scores	
 
 Exploratory	
 
 Effect of 5 once-weekly IV doses of SYNT001 on biomarkers including:           
 
CIC
 
C3
 
Serum anti-epithelial cell antibody (AECA) levels
 
Exploratory biomarkers (FCGR2A SNP, RNAseq, urine IgG)
 
Immune phenotyping by flow cytometry
 
 	Changes in CIC; C3; AECA levels by indirect immunofluorescence; FCGR2A SNP; RNAseq; urine IgG, CD3+CD4+ T, CD3+CD8+ T, monocytes, NK cells and B cells; urine IgG levels; changes in blood transcriptome	
 
 Concomitant Treatment	Corticosteroid use during the study	
 
 SYNT001 levels in skin biopsies	Measures of SYNT001 levels in skin biopsies	
  
 
Treatment-emergent AEs (TEAEs) will be summarized using the Medical Dictionary for Regulatory Activities (MedDRA®; Version 19 or higher) System Organ Class (SOC) and preferred term, classified from verbatim terms. The incidence and percentage of subjects with at least 1 occurrence of a preferred
	Objective	Endpoint	Primary		Safety and tolerability of 5 once-weekly IV infusions of SYNT001 to subjects with pemphigus vulgaris or foliaceus	AEs and clinical (safety) laboratory tests	Secondary		PK of SYNT001 following a 1-hour IV infusion	PK parameters: $t_{1/2}$ , $C_{max}$ , $T_{max}$ , $AUC_{0-24}$ , and $AUC_{0-\infty}$ .	Effect of 5 once-weekly IV doses of SYNT001 on: 
 
Total IgG (IgG1-4), IgA, IgM, and albumin
 
Serum anti-Dsg (1 and 3) antibodies
 
	Changes in levels of IgG, IgG subtypes (IgG1-4), IgA, IgM, albumin, serum anti-Dsg (1 and 3) antibodies	Assess immunogenicity	Anti-SYNT001 antibodies	Disease Activity	PDAI Scores	Exploratory		Effect of 5 once-weekly IV doses of SYNT001 on biomarkers including: 
 
CIC
 
C3
 
Serum anti-epithelial cell antibody (AECA) levels
 
Exploratory biomarkers (FCGR2A SNP, RNAseq, urine IgG)
 
Immune phenotyping by flow cytometry
 
	Changes in CIC; C3; AECA levels by indirect immunofluorescence; FCGR2A SNP; RNAseq; urine IgG, CD3 + CD4 + T, CD3 + CD8 + T, monocytes, NK cells and B cells; urine IgG levels; changes in blood transcriptome	Concomitant Treatment	Corticosteroid use during the study	SYNT001 levels in skin biopsies	Measures of SYNT001 levels in skin biopsies
Objective	Endpoint																								
Primary																									
Safety and tolerability of 5 once-weekly IV infusions of SYNT001 to subjects with pemphigus vulgaris or foliaceus	AEs and clinical (safety) laboratory tests																								
Secondary																									
PK of SYNT001 following a 1-hour IV infusion	PK parameters: $t_{1/2}$ , $C_{max}$ , $T_{max}$ , $AUC_{0-24}$ , and $AUC_{0-\infty}$ .																								
Effect of 5 once-weekly IV doses of SYNT001 on: 
 
Total IgG (IgG1-4), IgA, IgM, and albumin
 
Serum anti-Dsg (1 and 3) antibodies
 
	Changes in levels of IgG, IgG subtypes (IgG1-4), IgA, IgM, albumin, serum anti-Dsg (1 and 3) antibodies																								
Assess immunogenicity	Anti-SYNT001 antibodies																								
Disease Activity	PDAI Scores																								
Exploratory																									
Effect of 5 once-weekly IV doses of SYNT001 on biomarkers including: 
 
CIC
 
C3
 
Serum anti-epithelial cell antibody (AECA) levels
 
Exploratory biomarkers (FCGR2A SNP, RNAseq, urine IgG)
 
Immune phenotyping by flow cytometry
 
	Changes in CIC; C3; AECA levels by indirect immunofluorescence; FCGR2A SNP; RNAseq; urine IgG, CD3 + CD4 + T, CD3 + CD8 + T, monocytes, NK cells and B cells; urine IgG levels; changes in blood transcriptome																								
Concomitant Treatment	Corticosteroid use during the study																								
SYNT001 levels in skin biopsies	Measures of SYNT001 levels in skin biopsies																								

	
term will be included, using the most severe grade. The number of events per preferred term will also be summarized. Causality (relationship to study treatment) will be summarized separately.
 
TEAEs, SAEs, and AEs leading to withdrawal, or treatment discontinuation will be listed by subject, and cohort using SOC and preferred terms. Duration of AEs will be determined and included in listings, along with action taken, and outcome.
 
Laboratory results will be summarized by time point and cohort. The incidence of laboratory abnormalities will be summarized. The worst on-study grade after the first dose of study drug will be summarized. Results for variables that are not coded will be presented in the listings as below, within, and above the normal limits of the central laboratory. Vital sign measurements will be summarized by cohort at each scheduled time point using descriptive statistics.
 
Study drug concentrations will be used to calculate the following PK parameters: <math>t_{1/2}</math>, <math>C_{max}</math>, <math>T_{max}</math>, and area under the curve (AUC). PK parameters will be determined using non-compartmental method(s). Descriptive statistics of PK parameters for SYNT001 will include mean, standard deviation (SD), coefficient of variation (CV), median, minimum, and maximum. <math>T_{max}</math> will be reported as median and range. All descriptive statistics will be performed on untransformed PK parameters and after <math>\log_{10}</math> transformation of PK parameters.
 
PD results will be summarized by cohort. Descriptive statistics of PD parameters for SYNT001 will include mean, SD, CV, median, minimum, and maximum.
 
Immunogenicity results will be summarized by cohort. Descriptive statistics will include mean, SD, CV, median, minimum, and maximum.

--	--

**Table 1: Study Assessments**

Timepoint (Study Day)	Screen -14 to -1	0	1 (±1 hr)	2 (± 2 hr)	5 p (±4 hr)	7 (±4 hr)	12 p (±6 hr)	14 (±6 hr)	19 p (±6 hr)	21 (±6 hr)	28 (±6 hr)	29 (±1 hr)	30 (±2 hr)	33 (±4 hr)	42 (±3 day)	Follow-Up 56 (±5 days) or ET Visit	Extended Follow- up q
Informed Consent	X																
Demographics/Medical History	X																
Inclusion/Exclusion	X																
Physical Examination a	X	X				X		X		X	X				X	X	
Vital Signs b	X	X	X	X	X	X	X	X	X	X	X	X	X	X	X	X	
Pulse Oximetry c		X				X		X		X	X						
Clinical Safety Labs d	X	X				X		X		X	X			X	X	X	
Pregnancy test e	X	X														X	
Hepatitis & HIV Screen	X																
12-Lead ECG f	X	X					X				X					X	
Tetanus & VZV antibodies g		X														X	X
PDAI Score		X				X		X		X	X			X	X	X	
PK Sampling h		X	X	X	X						X	X	X	X			
Immunogenicity i		X						X			X					X	
Study Drug Administration j		X				X		X		X	X						
Immunoglobulins (IgG, IgA, IgM) and IgG subtypes (IgG 1-4) k	X	X	X	X	X	X	X	X	X	X	X	X	X	X	X	X	
CIC		X			X	X	X	X	X	X	X			X	X	X	
Anti-Dsg (1 & 3) antibody titer	X	X				X		X			X			X		X	
C3 and AECA l		X						X						X		X	
FCGR2A m		X															
RNAseq m		X						X						X		X	
Urine IgG m		X						X						X		X	
Immune phenotyping n		X									X						
Optional Skin Biopsy		X	X	X				X						X		X	
Photography o		X												X		X	
Adverse Events	To be collected from the date that the ICF is signed until 28 days after last dose of study drug.																
Concomitant Medications	To be collected from within 14 days prior to Day 0 through 28 days after last dose of study drug.																

ECG = electrocardiogram; ET= Early Termination; HIV = human immunodeficiency virus; ICF = informed consent form; PD = pharmacodynamic; PK = pharmacokinetic; VZV = varicella-zoster virus

- 
- a: Complete **PE**, including weight, to be performed. Height and BMI will be additional assessments conducted at screening.
- b: **Vital sign** measurements (sitting blood pressure, heart rate, respiratory rate, and oral temperature) to be obtained after 5 minutes of seated rest. Any abnormal measurements are to be repeated after 5 minutes of rest. On Days 0, 7, 14, 21, and 28 vital sign measurements will be collected immediately prior to the infusion; 15, 30, and 45 minutes after the start of the infusion; at completion of the infusion; and 30 minutes, 1 hour and 2 hours following completion of the infusion.
- c: **Pulse oximetry**: On Days 0, 7, 14, 21, and 28, pulse oximetry to be measured immediately prior to the infusion; 15, 30, and 45 minutes after the start of the infusion; at completion of the infusion; and 30 minutes, 1 hour and 2 hours following completion of the infusion.
- d: **Clinical safety labs**: hematology, clinical chemistry, and urinalysis (see [Section 6.7](#) for a complete list). Full clinical safety lab draws will be collected at Screening and on Days 0, 7, 14, 21, 28, 33, 42 and 56.
- e: **Pregnancy test**: To be performed at time of screening and prior to first dose of SYNT001 on Day 0 and on Day 56 (urine or serum test is acceptable, however, positive urine tests must be confirmed with serum testing.)
- f: Digital 12-lead **ECG** to be obtained after 5 minutes of rest in the supine position and in triplicate at least 1-2 minutes apart (see [Section 6.6](#) for additional information). On Days 0 and 28 to be obtained 5 minutes after the completion of infusion. Day 12 ECG will be collected only if the visit is conducted at the study site.
- g: **Serology**: Testing at Day 56 will not be done for any subject whose baseline titer is below the level of detection. If the Day 56 results are greater than 30% below the baseline value, or if the subject falls below the level of detection, the subject will be re-tested at 1 month after the Follow-Up visit (approximately 2 months after the subject's last dose); if still below the baseline value (or level of detection), the subject will be re-tested after another month (3 months after last dose). Any subject whose baseline value for tetanus or VZV was above the detectable level at baseline, and is not within 30% of the baseline value or is below the detectable level on Day 56 and upon 2 retests (2 and 3 months following last dose of SYNT001), will be referred to their primary care physician for further management. See [Section 6.7.3](#) for additional information.
- h: **PK**: Starting on Days 0 and 28, serum samples will be collected just prior to the start of study drug infusion (pre-dose), and at 5 minutes and 2, 4, 6, 24, and 48 hours after the end-of-study drug infusion. Additional samples will be collected on Days 5 and 33. See [Section 6.7.4](#) for additional information.
- i: **Immunogenicity**: Blood samples will be collected pre-dose when collected on dosing days. See [Section 6.7.6](#) for additional information.
- j: Prior to **study drug infusion**, SYNT001 drug product is to be diluted in Dextrose 5% in Water (D5W) to a total volume of 250 mL and administered intravenously over 1 hour using a 0.2-micron, inline filter. See [Section 9](#) for additional information.
- k: **Immunoglobulins (IgG, IgA, IgM) and IgG subtypes (IgG 1-4)**: Collected for measurements of IgG, IgG subtypes (IgG1-4), IgA, and IgM at every visit. On Days 0, 7, 14, 21, and 28, samples are collected prior to infusion of study drug. See [Section 6.7.5](#) for additional information
- l: Exploratory PD samples (C3 and AECA): collected pre-dose when collected on dosing days. See [Section 6.7.5](#) for complete information.
- m: Samples to be collected and stored; pending review of clinical and pharmacodynamics assessments
- n: Immune phenotyping by flow cytometry for measurement of CD3+CD4+ T, CD3+CD8+ T, monocytes, NK cells and B cells
- o: Photographs of active lesions taken prior to first dose on Day 0. Follow-up photographs will be taken at Days 33 and 56. Subjects who begin a steroid taper will have additional photographs taken at the clinic visit during which the decision to begin the taper is made.
- p: Visit Days 5, 12 and 19 may be conducted via at-home nursing in lieu of a subject visit to the study site.
- q: Extended follow-up visits will occur only if additional testing for anti-tetanus and/ or anti-VZV titers are required. These visits will occur as needed at approximately 2 months post last dose and 3 months post last dose.

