Cohort	No. of subjects	Dose								
1	8	SYNT001 10 mg/kg								
2	8	SYNT001 30 mg/kg								

	
On Day 0 photographs will be taken of active lesions. Follow-up photographs will be taken of the same areas on Days 33 and 56. If a subject begins a steroid taper, additional photographs will be taken at the clinic visit during which the decision to begin the taper is made.
 
Subsequent visits will occur on Days 1, 2, 5, 7, 12, 14, 19, 21, 28, 29, 30, 33, and 42 for safety assessments, study drug dosing, sample collections, and other study procedures.
 
Subjects also will return to the clinic on Day 56 (28 days after receiving their last dose of study drug) for an End-of-Study/Follow-Up visit.
 
See Table 1 for a schedule of all study events. To assess safety and tolerability, subjects will undergo physical examinations (PEs; including weight), vital sign measurements, clinical (safety) laboratory tests, adverse event (AE) assessments, concomitant medication assessments, and electrocardiograms (ECG).

Number of subjects
	
Approximately 16; two cohorts of 8 subjects each. An additional cohort of up to 8 subjects may be enrolled. Subjects who withdraw for any reason other than an AE and who do not receive study drug or have only received one dose of study drug may be replaced, up to one subject per cohort. The maximum number of subjects who may be enrolled in this study is 27 (24 + up to 3 replacements, as necessary). Within each dosing cohort, no more than 3 subjects with pemphigus foliaceus may be enrolled.

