
Safety assessments
	
Safety assessments include AEs, serious adverse events (SAEs), PEs, vital sign measurements, clinical safety laboratory evaluations, ECGs, and reasons for treatment discontinuations due to toxicity. Safety assessments will be performed at specified time points and prior to discharge from the clinic. Vital sign measurements, including blood pressure, pulse rate, respiratory rate, and temperature will be monitored throughout the study. Pulse oximetry will be monitored during the study drug infusion and for 2 hours following the end of the infusion.
 
The National Cancer Institute Common Terminology Criteria for Adverse Events (NCI CTCAE; Version 4.03) will be used for grading clinical and laboratory AEs.

	
The AE reporting period for a subject enrolled in the study begins when the subject provides informed consent and is continued for 28 days after the last dose of study drug. All AEs that occur in the enrolled subjects during the AE reporting period must be recorded, regardless of the relationship of the AE to study drug. Any known untoward event that occurs beyond the AE reporting period that the Investigator assesses as related to study drug should also be recorded.

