**7.11 Treatment Day 28 (Dose 5)**

On Day 28 ( $\pm 1$  Day), subjects will return to the clinic and the following procedures are to be performed prior to study drug infusion:

- Complete physical exam ([Section 6.3](#))
- Vital sign measurements (sitting blood pressure, heart rate, respiratory rate, oral temperature); to be measured immediately prior to the infusion ([Section 6.5](#))
- Pulse oximetry (to be measured immediately prior to the infusion) ([Section 6.5](#))
- Clinical safety laboratory tests (hematology, serum chemistry panel, urinalysis) ([Section 6.7](#))
- PDAI Score ([Section 6.4](#))
- PK sampling (collected just prior to the start of the study drug infusion; record collection date and time for each PK sample) ([Section 6.7](#))
- Immunogenicity sample collection (collected just prior to the start of study drug infusion) ([Section 6.7](#))
- PD sample collection (collected just prior to the start of the study drug infusion) ([Section 6.7](#))
  - IgG, IgG subtypes (IgG1-4), IgA, IgM
  - CIC
  - Immune phenotyping
- Concomitant medication assessment ([Section 6.9](#))
- AE assessment ([Section 6.10](#))

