### 7.16 Follow-up Day 56 (End-of-Study) or Early Termination Visit

On Day 56 ( $\pm 5$  days), subjects are to return to the clinic and the following procedures are to be performed:

- Complete physical exam ([Section 6.3](#))
- Vital sign measurements (after 5 minutes of rest; sitting blood pressure, heart rate, respiratory rate, oral temperature); abnormal results to be repeated after 5 minutes of rest ([Section 6.5](#))
- Clinical safety laboratory tests (hematology, serum chemistry panel, urinalysis) ([Section 6.7](#))
- Pregnancy test ([Section 6.7](#))
- 12-Lead ECG (to be obtained in triplicate after 5 minutes of rest in the sitting position) ([Section 6.5](#))
- Serum tetanus antibody and VZV antibody; Testing at Day 56 will not be done for any subject whose baseline titer is below the level of detection. See [Section 6.7.3](#) for additional information.
- Immunogenicity sample collection ([Section 6.7](#))
- PDAI Score ([Section 6.4](#))
- PD sample collection ([Section 6.7](#))
  - IgG, IgG subtypes (IgG1-4), IgA, IgM
  - CIC
  - Anti-Dsg (1 and 3) antibody titer
  - C3

- AECA
- RNAseq
- Urine IgG
- Optional skin biopsy ([Section 6.12](#))
- Photography ([Section 6.11](#))
- Concomitant medication assessment ([Section 6.9](#))
- AE assessment ([Section 6.10](#))

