### 9.6.2 Potential Immune Effects

An antibody blocking FcRn is anticipated to have several effects. These include acceleration of catabolism of IgG, but not other immunoglobulin isotypes such as IgA and IgM, leading to dose-dependent decreases in circulating IgG levels by up to an estimated 50% from the baseline levels after a single dose and further decreases after multiple doses up to a 70% to 80% reduction. Based on studies in humans, it is expected that with a single dose, the nadir of this effect will occur approximately 5 days after dosing. The time course of recovery of IgG following dosing in the Phase 1a study suggests that a return to within normal limits occurs within 4 weeks after a single dose and within 4 weeks after multiple doses as shown in NHPs.

Given the normal adult range of IgG of 700 to 1600 mg/dL (in some references), with a mean of 1150 mg/dL, a 50% decrease in the mean would be to 575 mg/dL and a 50% decrease from the low end of the normal range of 700 mg/dL would be to 350 mg/dL. An 80% decrease from baseline after multiple doses would result in IgG levels of 230 mg/dL and 140 mg/dL, respectively. While these levels are in the range found in patients with primary humoral immunodeficiency [[Ameratunga 2013](#)], the levels will be transient. Study subjects will be monitored clinically for any infection. Further, commercial IVIG can be given to reverse the low IgG levels in case of a bacterial infection occurring while their IgG levels are decreased.

An antibody blocking FcRn is expected to also down modulate innate and adaptive immunity and the catabolism of IgG-containing immune complexes (IC). Specifically, it is expected that anti-FcRn will promote the clearance of IgG-containing ICs and the effects of these IC on stimulating innate immune cell production of inflammatory cytokines (e.g., IL-12, interferon- $\gamma$ , and tumor necrosis factor [TNF]) and inhibit the processing and presentation of antigens contained within IC and thus the antigen-specific activation of CD4+ and CD8+ T-cells. Therefore, subjects with pre-existing conditions that are dependent upon IgG antibodies, such as chronic infections (e.g., HIV, HBV or HCV), will be excluded from this study, as will subjects with active infection in general.

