### 11.3.9.3 Information to be Provided by the Investigator

SAEs must be recorded on the SAE form in the EDC system. This requirement includes all SAEs that occur after informed consent and through 28 days after study drug dosing, and in addition, any SAE that are assessed as related to study treatment by the Investigator, even if the SAE occurs more than 28 days after study drug dosing.

The minimum information required for SAE reporting includes identity of Investigator, site number, subject number, an event description, SAE term(s), onset date, the reason why the event is serious (i.e., the seriousness criteria) and the Investigator's assessment of the relationship of the event to study treatment. Additional SAE information including medications or other therapeutic measures used to treat the event, action taken with the study treatment due to the event, and the outcome/resolution of the event will be recorded. Paper forms for reporting SAEs will be provided to the study sites as back-up in case the EDC system is not accessible.

In all cases, the Investigator should continue to monitor the clinical situation and report all material facts relating to the progression or outcome of the SAE. Furthermore, the Investigator may be required to provide supplementary information as requested by Syntimmune or designee.

When reporting an SAE, the following additional points should be noted:

- When the diagnosis of an SAE is known or suspected, the Investigator should report the diagnosis or syndrome as the primary SAE term, rather than as signs or symptoms. Signs and symptoms may then be described in the event description. For example, dyspnea should not be used as an SAE term if the diagnosis, which caused the dyspnea, is known to be malignant pleural effusion.
- Death should not be reported as an SAE, but as an outcome of a specific SAE, unless the event preceding the death is unknown. In the exceptional case where the events leading to death are unknown, then death may be used as an event term. If an autopsy was performed, the autopsy report should be provided.
- While most hospitalizations necessitate reporting of an SAE, some hospitalizations do not require SAE reporting, as follows:
  - Elective or previously scheduled surgery, e.g., a previously scheduled ventral hernia repair
  - Procedures for pre-existing conditions that have not worsened after initiation of treatment
  - Pre-specified study hospitalizations for observation

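### The ±5-day window on the Day 56 visit lets the last scheduled contact fall about 23 days after the last dose, before the 28-day safety collection period ends

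*Protocol*

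**What the plan says.** The 28-day period appears in several places:

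- Table 1, Adverse Events row: "To be collected from the date that the ICF is signed until 28 days after last dose of study drug". The Concomitant Medications row ends at the same point.
- Synopsis, Safety assessments: the AE reporting period starts at consent and "is continued for 28 days after the last dose of study drug".
- Section 11.3.9.3, on recording SAEs: "This requirement includes all SAEs that occur after informed consent and through 28 days after study drug dosing".
- Synopsis, Methodology (repeated in Section 4.3): "Subjects also will return to the clinic on Day 56 (28 days after receiving their last dose of study drug".
- Synopsis, duration: 14 days of screening, 28 of dosing and 28 of follow-up, 70 in all.

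The visit that closes the period is scheduled differently. Table 1 labels it "Follow-Up 56 (±5 days) or ET Visit". Section 7.16, headed "Follow-up Day 56 (End-of-Study) or Early Termination Visit", gives the same ±5 days around Day 56. Both attach the window to the study day, not to the date of the last dose.

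The Protocol gives two windows for the last dose: Day 28 ±6 hours in Table 1 and Day 28 ±1 day in Section 7.11.

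After the end-of-study visit, Section 7.17 and note q to Table 1 provide extended visits only where tetanus or varicella-zoster titres need retesting.

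**The concern.** Safety and tolerability are the primary objective, and the Protocol sets its own observation period at 28 days after the last dose. The visit that should close that period may be held before the period ends. A site that books it on Day 51 has no deviation to report, and nothing scheduled afterwards prompts it to ask the subject about the remaining days.

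An event that starts in those days is captured only if the subject volunteers it or the site calls on its own initiative. Capture in the tail of the period would then depend on when each visit was booked and on site habit. With 8 subjects per cohort, one subject is 12.5% of a cohort, so a single missed event would be visible in the incidence tables.

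**Working it through.** **Inputs.** End-of-study visit Day 56 ±5 days, so Day 51 to Day 61 (Table 1, Section 7.16). Last dose Day 28 ±6 hours (Table 1) or ±1 day (Section 7.11). Required AE, SAE and concomitant-medication collection: 28 days after the last dose.

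**Plan's own figures.** Nominal interval from last dose to final visit: 56 − 28 = 28 days. Total participation: 14 + 28 + 28 = 70 days. Both agree with the Protocol.

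**Shortest compliant interval** = (56 − 5) − day of last dose. **Shortfall** = 28 − that interval.

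| Last dose given | Interval to a Day 51 visit | Shortfall | Share of 28 days |
|---|---|---|---|
| Day 28, on time | 51 − 28 = 23 days | 5 days | 5/28 = 17.9% |
| Day 28 + 6 h (Table 1 limit) | 51 − 28.25 = 22.75 days | 5.25 days | 5.25/28 = 18.75% |
| Day 29 (Section 7.11 limit) | 51 − 29 = 22 days | 6 days | 6/28 = 21.4% |

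**Longest compliant interval** = (56 + 5) − day of last dose: 61 − 28 = 33 days on time, 61 − 27.75 = 33.25 days under Table 1, and 61 − 27 = 34 days under Section 7.11.

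**Does anything else cover the gap?**

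- Extended follow-up visits (Section 7.17) depend on the titre results and serve only those subjects.
- Section 11.4.3 requires the status of continuing AEs to be documented as of 28 days after dosing, and follow-up visits for subjects who have AEs. That reaches events already known at the final visit. It schedules no enquiry about events that begin after it.
- No telephone call or other contact is scheduled after the end-of-study visit.

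**Would removing only the early side be enough?** With Day 56 −0/+5, the shortest interval is 56 − 28 = 28 days if the dose was on time, 56 − 28.25 = 27.75 days under Table 1 and 56 − 29 = 27 days under Section 7.11. Only a window counted from the actual last dose guarantees 28 days in every case.

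**The case against.** The strongest reply is that the collection period is fixed independently of the visit. Events through day 28 must be recorded whatever the visit date, Section 11.4.3 deals with continuing events, and the Synopsis and Section 4.3 themselves describe the visit as 28 days after the last dose. A careful site would therefore schedule it that way or call the subject. This stands as far as it goes: the AE period is not shortened, and Day 51 is the last scheduled contact, not necessarily the last contact. The reply does not supply a scheduled way of learning about new events after an early visit.

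A second objection is that the 22-day interval and the 21% share rest on Section 7.11 alone. That also stands. Under Table 1 the shortfall is 5 to 5.25 days. The two dose windows contradict each other and have to be reconciled.

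A reader might go further and infer that the Day 56 sample is meant to prove IgG recovery at four weeks, so that an early visit would misclassify subjects. The documents do not support this. Section 9.6.2 does state "a return to within normal limits occurs within 4 weeks after a single dose and within 4 weeks after multiple doses as shown in NHPs", but this is background on risk, it gives an upper bound, and its multiple-dose part comes from animals. The Protocol defines no category of recovered subjects.

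Nor can one show that the visit date decides who is retested. The 30% trigger in Section 6.7.3 applies to tetanus and varicella-zoster titres, for which the Protocol gives no recovery curve, and referral requires failure on Day 56 and at two later retests.

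**Conclusion.** The point holds as a gap in scheduled safety contact. A compliant final visit can fall 23 days after an on-time last dose, and 22.75 days at Table 1's dose limit, against a required 28. That leaves 5 to 5.25 days, about 18–19% of the period, with no planned enquiry about new events. If Section 7.11's dose window governs, the worst case is 22 days and a 6-day gap.

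These are limits of what the windows permit. They do not forecast how often early visits occur, and the documents give no basis for estimating how many events would be missed. The 5-day shortfall needs nothing beyond Table 1. The point is modest in size, but it bears on the primary objective and can be closed at almost no cost.

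**What to change.** In Table 1 and Section 7.16, define the scheduled end-of-study visit as 28 to 33 days after the actual last dose. For a subject dosed on Day 28 this is Day 56 to Day 61, so the latest permitted day does not change. Leave the early-termination use of the same column unchanged. A bare 0/+5 window on Day 56 is not sufficient, for the reason shown in the working.

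Separately, reconcile the Day 28 dose window between Table 1 and Section 7.11. A visit counted from the actual last dose gives 28 days whichever is retained.

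The change is one entry in Table 1 and one in Section 7.16. Sites lose the option of an early final visit, and some subjects attend a few days later than they otherwise would. No assessment is added.
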